### **7.18.1. Chemistry, Hematology, and Urinalysis (Laboratory Safety Evaluations)**

Laboratory tests for chemistry, hematology, and urinalysis are specified in [Table 4](#). Patients do not need to fast prior to laboratory safety tests.

Analysis of hematology and chemistry will be performed by the central laboratory chosen by the Sponsor. A urine dipstick and urine pregnancy test (for women of childbearing potential) will be performed at the site (supplied by the central laboratory). A sample for urinalysis (including microscopy [RBCs, WBCs, epithelial cells, and bacteria]) AND urine culture will be sent to the central laboratory only if the urine dipstick tests positive for the presence of leukocytes, nitrites, or blood cells. If a patient reports symptoms that are suggestive of a urinary tract infection at any visit, a urine dipstick should be performed and a sample sent for urinalysis and culture, as needed.

If all laboratory values are within the normal reference range, the patient may continue to be evaluated for study entry. If one or more values fall outside the normal range, the Investigator may either exclude the patient from the study or investigate further to determine clinical relevance. Please refer to [Appendix 2](#) for an algorithm for assessing out-of-range laboratory values.

**Table 4 Laboratory Tests**

Hematology	Chemistry	Urinalysisa	Other
Hematocrit	Albumin	Blood	Serum $\beta$ -human chorionic gonadotropin ( $\beta$ -hCG) b
Hemoglobin	Alkaline phosphatase	Glucose	
Platelet count	Alanine aminotransferase (ALT)	Protein	
WBC (total and differential)	Aspartate aminotransferase (AST)	Specific gravity	
RBC	Bicarbonate	Microscopic exam, (RBCs, WBCs, epithelial cells, and bacteria)	
	Calcium	pH	
	Chloride	Color	
	Creatinine c	Urine pregnancy test ( $\beta$ -hCG)	
	Glucose (fasting or non-fasting)		
	Potassium		
	Sodium		
	Total Bilirubin		
	Direct Bilirubin d		
	Blood Urea Nitrogen		
	Total Cholesterol		

a. A sample for urinalysis and urine culture will be sent to the central laboratory only if the urine dipstick performed at the site tests positive for the presence of leukocytes, nitrites, or blood cells.

b. Urine  $\beta$ -hCG will be tested for women of childbearing potential only. If urine  $\beta$ -hCG is positive, a serum  $\beta$ -hCG must be performed.

c. eGFR will be calculated and reported by the central lab.

d. If total bilirubin is elevated above the upper limit of normal.

### **7.18.2. Urine $\beta$ -hCG**

Women of childbearing potential only must have a urine  $\beta$ -hCG pregnancy test at each study visit indicated on the Schedule of Activities (Section 1.1). A urine pregnancy test (supplied by the central laboratory) will be performed at the site. A positive urine  $\beta$ -hCG test must be followed up with a serum  $\beta$ -hCG pregnancy test. A positive pregnancy test prior to randomization requires exclusion. A positive urine  $\beta$ -hCG test after randomization requires immediate interruption of Study Treatment until a serum  $\beta$ -hCG is performed and found to be negative. Patient must be discontinued from the study and followed if pregnancy is confirmed by a positive serum  $\beta$ -hCG.

### **7.19. IxRS Randomization to Study Treatment**

Assignment of patients to double-blind Study Treatment in this study is described in Section 4.1 and Section 6.3. The Study Treatment assignments will be managed/recorded via the IxRS.

### **7.20. Dispense Double-Blind Study Treatment**

At the Week 12, 16, 24, 36 and 44 Visits, double-blind Study Treatment will be dispensed to patients, as described in Section 6, and according to their randomized treatment assigned per IxRS.

### **7.21. Study Treatment Return/Accountability Review**

Patients should bring all unused study drug to each study visit. A complete tablet/capsule count will be performed, and results will be recorded as the primary source of patient Study Treatment compliance. Tablet/capsule counts will also be recorded in the IxRS. All patients should be reinstructed regarding dosing compliance during study visits. The authorized study personnel conducting the re-education must document the process in the patient's source records.

### **7.22. Follow-up Visit**

The Follow-up Visit should be performed 28 days after the patient's last dose of Study Treatment to collect information about any serious adverse events that occurred during this period. For a patient who discontinues Study Treatment early, the Follow-up Visit should occur 28 days after the last dose of Study Treatment. However, if the discontinuation visit occurs  $\geq 28$  days after the patient's last dose of Study Treatment, that visit will serve as the Follow-up Visit. Safety labs may be collected for the evaluation of adverse experiences during discontinuation at the discretion of the Investigator.

## 8. SAFETY CONSIDERATIONS

Study assessments of safety include adverse events, physical examinations, vital signs (and weight), and clinical laboratory tests.

### 8.1. Definition of an Adverse Event

An adverse event is any untoward medical occurrence in a patient or clinical investigation patient, temporally associated with the use of a medicinal product, whether or not considered related to the medicinal product.

An adverse event can therefore be any unfavorable and unintended sign (including an abnormal laboratory finding), symptom, or disease (new or exacerbated) temporally associated with the use of a medicinal product or protocol-specified procedure, whether or not considered related to the medicinal product or protocol-specified procedure. Any worsening (i.e., any clinically significant adverse change in frequency and/or intensity) of a preexisting condition that is temporally associated with the use of the Sponsor's product, is also an adverse event.

Events meeting the definition of an adverse event **include**:

- A worsening, excluding minor fluctuations, in the nature, severity, frequency, or duration of a pre-existing condition;
- A new condition detected or diagnosed after investigational product administration even though it may have been present prior to the start of the study;
- Injury or accidents: If a medical condition is known to have caused the injury or accident, the medical condition and the accident should be reported as 2 separate medical events (e.g., for a fall secondary to dizziness, both "dizziness" and "fall" should be recorded separately);
- An investigational abnormality (e.g., laboratory parameter, vital sign, ECG) only if the abnormality is considered clinically significant by the Investigator based on at least one of the following criteria:
  - Induces clinical signs or symptoms;
  - Requires active intervention;
  - Requires interruption or discontinuation of Study Treatment.
- Signs, symptoms, or the clinical sequelae of a suspected interaction.
- Signs, symptoms, or the clinical sequelae of a suspected overdose of either investigational product or a concomitant medication.
- Events that **do not** meet the definition of an adverse event include:
- The disease/disorder being studied, or expected progression, signs, or symptoms of the disease/disorder being studied, unless more severe than expected for the patient's condition;
- Medical or surgical procedure (e.g., endoscopy, appendectomy) should be entered into the electronic case report form (eCRF). If not planned prior to signing the informed consent, the condition that leads to the procedure is reported as an adverse or serious event, as appropriate. Periodic procedures for routine maintenance of a medical device

should not be considered associated with an adverse event (e.g., expected change of a stent);

- Situations where an untoward medical occurrence did not occur (e.g., planned hospitalization for an elective procedure, with elective defined as known or planned at the time of signing of the informed consent; social and/or convenience admission to a hospital);
- Anticipated day-to-day fluctuations of pre-existing disease(s) or condition(s) present or detected at the start of the study that do not worsen.

Adverse events that occur during the study should be evaluated by the Investigator and assessed for causal relationship to Study Treatment and severity, as described in Section 8.4 and Section 8.5. Episodic adverse events, such as vomiting, or those that occur repeatedly over a period of consecutive days are “intermittent”. All other events are “continuous”. Additional information on detecting, documenting, and reporting adverse events and serious adverse events are provided below. No toxicity-related dose reductions of Study Treatment are permitted; however, Study Treatment can be held for a period of up to 21 days for evaluation and treatment of an adverse event. The Study Treatment may be restarted if deemed safe for the patient by the Investigator.

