### **5.4. Interruption of Study Treatment**

#### **5.4.1. Temporary Interruption**

The medical monitor should be contacted for Study Treatment interruption of > 7 days in duration. Study treatment may be temporarily interrupted for up to 21 consecutive days if required for adverse event management, as described in Section 6.6.

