## **6.6. Treatment Discontinuation and Rechallenge**

Refer to Section 8.6.1 and Section 8.6.2, respectively, for information regarding temporary interruption or permanent discontinuation of Study Treatment in association with liver test abnormalities.

Patients who experience a grade 3 or greater toxicity that is considered related to Study Treatment should have their treatment discontinued permanently.

Patients who experience a grade 3 or 4 adverse event that is not related to Study Treatment may have their Study Treatment interrupted for a period of up to 21 consecutive days if the Investigator believes it is in the best interest of the patient. (Refer to Table 5 for Criteria for

Determining the Grade/Severity of Adverse Event Terms). Prior to restarting Study Treatment, the adverse event must have improved to grade 0, 1, or 2.

If the adverse event that is not related to Study Treatment remains grade 3 or grade 4 after treatment interruption or the Investigator believes it is in the best interest of the patient, Study Treatment should be discontinued permanently.

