#### **8.6.1. Criteria for Temporary Withholding of Study Treatment in Association with Liver Test Abnormalities**

Elevated liver enzymes or bilirubin sufficient to require withholding study medication must be reported **within 24 hours of the study site personnel's knowledge of the event** using AECl specific CRFs/forms/worksheets provided for the study.

Hepatic enzymes will be monitored in accordance with FDA drug-induced liver injury guidelines [FDA, 2009].

If the following liver test abnormalities develop, Study Treatment should be withheld immediately with appropriate clinical follow-up (including repeat laboratory tests, until a patient's laboratory profile has returned to normal/baseline status), and the event reported as a serious adverse event:

- ALT or AST > 8 x ULN; or
- ALT or AST > 5 x ULN and persists for more than 2 weeks; or
- ALT or AST > 3 x ULN and total bilirubin > 2 x ULN or international normalized ratio (INR) >1.5
- ALT or AST > 3 x ULN with appearance of fatigue, nausea, vomiting, right upper quadrant pain or tenderness, fever, rash and/or eosinophilia (>5%).

Rechallenge may be considered if an alternative cause for the abnormal liver tests (ALT, AST, total bilirubin) is discovered and the laboratory abnormalities resolve to normal or baseline values. The Investigator and Sponsor must discuss and agree with any decision to rechallenge.

Rechallenge should not occur when the etiology of the liver test abnormalities is considered possibly drug induced.

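### Section 8.1 lets the Investigator restart treatment after any adverse event, without the limits in Section 6.6 for grade 3 or greater events

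*Protocol*

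**What the plan says.** The closing paragraph of Protocol Section 8.1 tells the Investigator to assess each adverse event for causality and severity, and points to Sections 8.4 and 8.5 for this. It rules out dose reductions for toxicity and offers an interruption in their place: "Study Treatment can be held for a period of up to 21 days for evaluation and treatment of an adverse event". The next sentence gives the condition for resuming: "The Study Treatment may be restarted if deemed safe for the patient by the Investigator".

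Section 6.6, which is headed for treatment discontinuation and rechallenge, is narrower. For related events: "Patients who experience a grade 3 or greater toxicity that is considered related to Study Treatment should have their treatment discontinued permanently". For unrelated grade 3 or 4 events it allows an interruption of up to 21 consecutive days, with this condition: "Prior to restarting Study Treatment, the adverse event must have improved to grade 0, 1, or 2". If the unrelated event stays at grade 3 or 4, treatment should be stopped for good.

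Section 5.4.1 repeats the 21-day allowance but ties it to 6.6: "Study treatment may be temporarily interrupted for up to 21 consecutive days if required for adverse event management, as described in Section 6.6". Section 5.4.2, on rechallenge, only refers the reader to 6.6.

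Section 8.6.1 has its own rules for the listed liver test abnormalities: "The Investigator and Sponsor must discuss and agree with any decision to rechallenge", and "Rechallenge should not occur when the etiology of the liver test abnormalities is considered possibly drug induced".

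**The concern.** Section 8.1 does more than define terms. Its last two sentences tell the site what it may do with study treatment when an adverse event occurs. They come straight after the instruction to grade the event and judge its cause, yet the restart permission uses neither assessment. Of the places outside 6.6 that address an interruption for adverse events in general, 5.4.1 cites 6.6 and 8.1 does not. The permanent stop for related grade 3 or greater toxicity is not repeated in Section 8, where a site would look when handling an adverse event.

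At stake is re-exposure of a patient to a drug after a severe reaction already judged related to it, in a study whose primary objective is safety and tolerability. The statistical analysis is not affected.

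**Working it through.** No figure is involved, so the check sets the rules side by side for each type of event. Inputs are the current texts of Sections 5.4.1, 5.5, 6.6, 8.1, 8.6 and 8.6.1.

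| Event | Section 8.1 read alone | Specific rule | Do they agree? |
|---|---|---|---|
| Related, grade 3 or greater and survivable | Hold up to 21 days, restart if the Investigator judges it safe | 6.6: should be stopped permanently | No, opposite actions |
| Unrelated, grade 3 or 4 | Same | 6.6: restart only after improvement to grade 0, 1 or 2; otherwise stop permanently | No, a required condition is missing from 8.1 |
| Liver test abnormality listed in 8.6.1 | Same | 8.6.1: Investigator and Sponsor must agree; no rechallenge if possibly drug induced | 8.1 is silent, but 8.6.1 has its own protection (below) |
| Grade 1 or 2, not hepatic | Same | None stricter | Yes |

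**Length of hold.** The 21-day maximum is the same in 5.4.1, 6.6 and 8.1, and 5.5 requires discontinuation beyond 21 consecutive days. The sections differ on who may restart and under what condition, not on duration.

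**Liver events.** Section 8.6.1 requires that treatment be withheld at once, that the event be reported within 24 hours and that it be reported as a serious adverse event. Under 8.3.2, marking an event as serious automatically notifies the Sponsor. A liver case is therefore unlikely to be handled on 8.1 alone.

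**Other events.** Serious events reach the Sponsor by the same automatic notification, and adverse events of clinical interest are reported within 24 hours under 8.6. What remains is mainly a related grade 3 event that is neither. Table 5 makes this possible, because grade 3 includes events that limit self-care without being life-threatening. The group is small, since the other grade 3 descriptors (hospitalization indicated, disabling) overlap the seriousness criteria in 8.2.

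**The case against.** The strongest reply is that the protocol must be read as a whole. Section 10.9.2 holds the Investigator to the entire document. Section 6.6 is the section on this subject, 5.4.1 and 5.4.2 send the reader there, and 6.6 itself points to 8.6.1 and 8.6.2. The wording of 8.1 is permissive, so a site that follows 6.6 breaches nothing in 8.1. A specific rule normally controls a general one. The summary of changes also shows the intent: version 2.0 removed rechallenge after related grade 3 or higher events from 6.6. That entry is background only, and the point rests on the current text.

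This stands as far as weight is concerned, and it is why the point is minor. It does not remove the difference. Section 8.1 nowhere says that it yields to 6.6, and a rule on when to stop a drug should not depend on the reader inferring precedence.

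A reader might infer three stronger things that the protocol does not support:

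- *That the protocol as a whole permits restart after a related grade 3 event.* It does not; 6.6 is clear. Only 8.1 read by itself does so.
- *That the liver limits are equally exposed.* They are not. Section 8.6.1 imposes immediate withholding and serious-event reporting, so the omission from 8.1 has little practical effect there.
- *That 8.1 is the reason short holds escape medical monitor review.* The threshold is set in 5.4.1: "The medical monitor should be contacted for Study Treatment interruption of > 7 days in duration". It applies equally to a hold made under 6.6, and changing 8.1 would not alter it.

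**Conclusion.** The point holds as a minor inconsistency in an operative safety instruction. Section 8.1 gives an unqualified permission to hold and restart. For a related grade 3 or greater toxicity it conflicts with 6.6, and for an unrelated grade 3 or 4 event it leaves out a condition that 6.6 makes mandatory. For grade 1 or 2 non-hepatic events there is no conflict.

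The exposure depends on a site acting on 8.1 without consulting 6.6, and it is mainly confined to related grade 3 events that are neither serious nor of clinical interest. The protocol gives no rate of related grade 3 or greater events, so no count of patients can be derived; it may be zero. Confidence is high that the text omits these limits. Whether any patient would be affected is not known.

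**What to change.** Keep the two existing sentences and add only a qualifier. After the clause that rules out dose reductions, read: *however, subject to Sections 6.6, 8.6.1 and 8.6.2,* "Study Treatment can be held for a period of up to 21 days for evaluation and treatment of an adverse event". Then: *Subject to the same sections,* "The Study Treatment may be restarted if deemed safe for the patient by the Investigator".

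The phrase that limits the hold to evaluation and treatment of an adverse event should stay, because dropping it would widen the permission to holds for any reason. The 6.6 rules need not be copied into 8.1; a cross-reference avoids a second text to keep aligned. The change adds no clinical rule and leaves 8.1 in force as it stands for grade 1 or 2 non-hepatic events.

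The cost is one qualifier and no change to data collection or analysis. Because Section 10.6 requires ethics committee submission and approval of any protocol modification, it can be made with the next amendment rather than as an amendment of its own.

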## 8.2. Definition of a Serious Adverse Event

If an event is not an adverse event per Section 8.1, then it cannot be a serious adverse event if serious conditions are met (e.g., hospitalization for signs/symptoms of the disease under study, death due to progression of disease, etc.). A serious adverse event is any untoward medical occurrence that, at any dose:

- a. Results in death
- b. Is life-threatening
- c. NOTE: The term 'life-threatening' in the definition of 'serious' refers to an event in which the patient was at risk of death at the time of the event. It does not refer to an event, which hypothetically might have caused death, if it were more severe.
- d. Requires hospitalization or prolongation of existing hospitalization
- e. NOTE: In general, hospitalization signifies that the patient has been detained (usually involving at least an overnight stay) at the hospital or emergency ward for observation and/or treatment that would not have been appropriate in the physician’s office or out-patient setting. Complications that occur during hospitalization are adverse events. If a complication prolongs hospitalization or fulfills any other serious criteria, the event is serious. When in doubt as to whether “hospitalization” occurred or was necessary, the adverse event should be considered serious.
- f. Hospitalization for elective treatment of a pre-existing condition that did not worsen from baseline is not considered an AE.
- g. Results in disability/incapacity
- h. NOTE: The term disability means a substantial disruption of a person’s ability to conduct normal life functions. This definition is not intended to include experiences of relatively minor medical significance such as uncomplicated headache, nausea, vomiting, diarrhea, influenza, and accidental trauma (e.g., sprained ankle) which may

interfere or prevent everyday life functions but do not constitute a substantial disruption.

- i. Is a congenital anomaly/birth defect
- j. Medical or scientific judgment should be exercised in deciding whether reporting is appropriate in other situations, such as important medical events that may not be immediately life-threatening or result in death or hospitalization but may jeopardize the patient or may require medical or surgical intervention to prevent one of the other outcomes listed in the above definition. These should also be considered serious. Examples of such events are invasive or malignant cancers, intensive treatment in an emergency room or at home for allergic bronchospasm, blood dyscrasias or convulsions that do not result in hospitalization, or development of drug dependency or drug abuse.

### **8.3. Adverse Event Reporting**

The Investigator or site staff is responsible for detecting, documenting, and reporting events that meet the definition of an adverse event or serious adverse event.

The reporting of serious adverse events by the Sponsor (Urovant Sciences GmbH) to regulatory authorities is a requirement and each authority has a timetable for reporting these events based upon established criteria. Likewise, it is the responsibility of the Investigator to report serious adverse events to their local IRB, REB, or IEC, as required by their local IRB/REB/IEC requirements.

Care will be taken not to introduce bias when detecting adverse events and/or serious adverse events. Open-ended and non-leading verbal questioning of the patient is the preferred method to inquire about adverse event occurrence. Appropriate questions include:

- • “How are you feeling?”
- • “Have you had any (other) medical problems since your last visit/contact?”
- • “Have you taken any new medicines, other than those provided in this study, since your last visit/contact?”

The patient’s diary entries and responses to questionnaires used in the study will not be used as a primary means to collect adverse events however, they should be reviewed by the study site personnel and the study monitors. Should the Investigator or site staff become aware of a potential adverse event through the information collected with these instruments, proper follow-up with the patient for medical evaluation should be undertaken. Through this follow-up, if it is determined that an adverse event not previously reported has been identified, normal reporting requirements should be applied.

All patients who experience an adverse event will be evaluated at appropriate time intervals and followed until the event resolves, becomes stable or chronic, or the patient is deemed lost to follow-up. At the conclusion of the study, the Investigator and medical monitor will assess unresolved adverse events and determine if additional/continued follow-up is warranted.

All adverse events, whether related to the Study Treatment or not, must be fully and completely documented on the adverse event case report form and in the patient’s source documents. In addition, any adverse event resulting in permanent treatment discontinuation must be recorded

on the appropriate case report form as well as documented in the patient's source documents. Adverse event terms should include a diagnosis, as available, in preference to listing the individual signs and symptoms. If the diagnosis is not known, the Investigator should record each sign and symptom as an individual adverse event.

Reporting for overdose and for pregnancy in the patient or patient's partner will be reported as described in Section 8.3.3 and Section 8.7, respectively.

